6.3 Datasets or Population Analyzed

The dataset will consist of all enrolled subjects. This excludes all patients who failed the screening for this study or those who were eligible but uninterested in study participation. The primary efficacy analysis will be done with an intention-to-treat sample per protocol.

6.4 Handling of Missing data

If data are missing, the absence of data will be handled in a manner consistent with current expert recommendations, some of which have been established by our own team.³⁻⁶ Our approach emphasizes either maximum likelihood or multiple imputation. All participants who dropped out will be included in all analyses up to the time of withdrawal.

6.5 Safety Analysis

While we anticipate a very low rate of adverse events, the medical monitor will compare AEs and SAEs between the two arms. We will conduct this analysis to inform the Phase II clinical trial of this intervention.

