The research coordinator (RC) will provide the Pillsy device and orient the participants in the use of the Pillsy app. Participants in both groups will also have full access to services normally provided by the prescribing office including blood testing and counseling services (i.e. SAU). All participants will receive the Pillsy cap (to track and time stamp pill bottle openings, closings, etc). The participants assigned to the Pillsy intervention, will also have a mobile phone reminder application. If the participant does not take their medicine at the correct time, a light on the smart pill cap will flash. If the bottle is not opened within 20 minutes, the Pillsy app sends an SMS text message to participant's phone. If the bottle is not opened within 60 minutes, the participant then receives an automated phone call. The participant may also receive brief motivational phrases or craving surveys that can be tailored to participant needs and preferences.

Pillsy also includes a Pillsy Helpers feature in which the participant can name friends and family members who will also receive a text message notification one hour after a missed dose. If the participant is struggling, his or her social support can attempt to contact the participant. The MAT prescriber may also be a Pillsy Helper. The MAT prescriber may be contacted when the participant has missed a dose if they are designated as a helper, giving the prescriber the opportunity to intervene. Providers may decide to call the imminently nonadherent participant to provide a brief, timely therapeutic intervention for which the provider can bill using the 99091 CPT code.

All data handling will conform to appropriate regulatory guidelines (HIPAA) and will be collected in such a way that it can be integrated into existing EMRs. The long-term goal is for this information to be available to one's prescriber and provider in real-time for monitoring.

Participants in SAU arm will receive a prescription for BUP/NAL tablets/sublingual films and any services normally provided by the prescribing office. Participants in SAU arm will receive an inactive Pillsy smart cap that will track openings but will not provide reminders or any other messaging.

Primary Endpoint

Adherence to BUP/NAL treatment assessed by medication possession ratio (pills taken/pills prescribed)

Secondary Endpoints

1. Participant engagement quantified through office visits and assessed via real time surveys

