5. STUDY ASSESSMENT AND PROCEDURES

This will be a collaborative study between Washington State University, Pillsy, Inc, and the clinical site Ideal Option (opioid and other substance use disorders treatment center). The overarching goal is to evaluate if the use of the Pillsy system will improve treatment adherence. The study coordinator will work closely with the medical assistant from the clinical site, conducting a scripted screening, by phone or in person, documenting substance use, addiction treatment history, medical and psychiatric history, medications and availability of social support. Only patients recently initiating BUP/NAL treatment will be approached to assess their eligibility for the study.

The clinical site will be responsible for the BUP/NAL prescription and treatment plan. Participants will receive their prescription medications through their normal pharmacy. Pillsy, though the RC will provide the Pillsy system which includes the smart bottle cap (Pillsy Cap), the mobile application (Pillsy App), and the SMS texting platform with a brief training on how to utilize the system. Pillsy Cap tracks when the bottle is opened or closed. Figure 1 (below) is a draft CONSORT diagram of participant flow through the study protocol.

[figure not shown]

Figure 1. Overview of study Procedures and CONSORT Diagram for Participant Flow.

Intervention

Participants will be directed to preferably bring their pill bottle and medication in for their baseline visits. While it is possible for us to orient participants to the intervention before they have received their prescription or after even if they don't have the bottle, this lessens the training experience substantially and could decrease the utility of the cap and efficacy of the system. The RC will orient the participants in the use of the Pillsy app. The participants in both groups will also have full access to the services normally provided by the prescribing office including blood testing and counseling services. The Pillsy intervention consists of a Smart Pill Cap and a mobile phone application. All participants will receive the Pillsy cap (to track pill bottle openings), but only the active group will receive the Pillsy app with messaging and reminders. Please note this when reading the below, since the below is what the PLY group will receive, but not the SAU group.

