If the patient does not take their medicine at the correct time, a light on the smart pill cap begins to flash. If the bottle is not opened within 20 minutes, the Pillsy application sends an SMS text reminder to the patient's phone. If the bottle is not opened within 60 minutes, the patient receives an automated phone call. The patient may also receive brief motivational phrases that can be tailored to patient needs and preferences. Pillsy also includes a "Pillsy Helpers" feature in which the patient can name friends and family members who will also receive a text message notification one hour after a missed dose. Thus, if the patient is struggling, his or her support system can attempt to contact the patient and offer motivation. Importantly, as proposed in the clinical trials detailed in this application, the MAT prescriber can also be a Pillsy Helper.

All data handling will conform to meet HIPAA requirements, including administrative, physical, and technical safeguards. Data will be encrypted in storage and in rest in REDCap with regularly scheduled data deposits from Pillsy into REDCap.

Participants in the service as usual (SAU) arm will receive a prescription for BUP/NAL tablets/sublingual films and any services normally provided by the prescribing office. Participants in the SAU arm will receive an "inactive" Pillsy smart cap that will track openings but will not provide reminders or any other messaging.

Screening Visit

The RC will screen the patient to assess the participant's appropriateness for the study. If the prospective participant meets inclusion/exclusion criteria, the RC will explain the clinical study in detail and informed consent will be obtained. If eligible, the participant will be trained on how to use the Pillsy system (cap and app) if randomized to PLY group. No training will be needed for the SAU. While their cap will be activated to capture open and close times, that is the only data that will be collected on the cap. and randomized to one of the study groups.

Week 1 Assessment

Study participants will return to office as frequently as the prescriber sees fit in the course of addiction treatment. At 1 week +/- 1 day, the RC will count BUP/NAL tablets/sublingual films and compare to the prescribed number of pills for that period. Participants will complete questionnaires.

Week 6 Assessment

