5.1.1 Adverse events (AE)

According to the code of federal regulation title 21 of the Food and Drug Administration (FDA), an Adverse event refers to any untoward medical occurrence associated with the use of a drug in humans, whether considered drug related or not.

All AEs, whether volunteered, elicited, or noted on physical examination, will be recorded throughout the study (i.e., from signing of the ICF until completion).

All AEs will be collected in and recorded in REDCap.

Classification of an Adverse Event

Severity of event

Each AE will be assigned a category by the Investigator as follows:

Mild: An AE that is easily tolerated by the subject, requires minimal or no treatment and does not interfere with the participant's daily activities.

Moderate: An AE that results in a low level of inconvenience or concern by therapeutic measures. Moderate events may cause some interference with functioning. Intervention may be needed.

Severe: An AE that prevents normal everyday activities and may require systemic drug therapy or other treatment. Severe events are usually potentially life-threatening or incapacitating. If there is a change in severity of an AE, it must be recorded as a separate event.

Relationship of Event

The Investigator will make every effort to assess the relationship of the AE, if any, to the study intervention. The Investigator should use knowledge of the subject, the circumstances surrounding the event, and an evaluation of any potential alternative causes to determine

whether an AE is related to the study treatment. Causality should be assessed using the categories presented below:

Related: The AE is known to occur with the study intervention, there is a reasonable possibility that the study intervention caused the AE, or there is a temporal relationship between the study intervention and event. "Reasonable possibility" means that there is evidence to suggest a causal relationship between the study intervention and the AE.

Not Related: There is no reasonable possibility that the administration of the study intervention caused the event. There is no temporal relationship between the study intervention and event onset, or an alternate etiology has been established.

Action Taken

The investigator will describe the action taken in the appropriate section in REDCap, as follows:

- None
- Study procedure or medication stopped
- Study medication temporarily interrupted
- Concomitant medication
- Other, specify

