The risk to patients from the digital intervention is negligible. The potential benefit of the intervention is improved adherence to opioid agonist/antagonist therapy specifically and medication-assisted therapy in general. This benefit may occur in the patients participating in the trial, and the data collected may extent to future users of the technology.

Medication-assisted therapy is our best hope for combatting the opioid crisis in the near term. Adherence to opioid agonist/antagonist therapy is critical. Pillsy is a technology that can improve adherence to opioid agonist/antagonist therapy and thereby could help curb the current opioid crisis. Since Pillsy is a digital intervention, no physical adverse events are anticipated. However, participants will be undergoing medication-assisted therapy during their clinical care. Patients will be monitored by their respective provider for drug-related adverse events as they would during clinical care. If a provider decides to stop BUP/NAL for any reason (including, but not limited to, a treatment-related adverse event), the participant will also be discontinued from the Pillsy intervention. RCs will attempt to gather subjective feedback about the Pillsy intervention from discontinued participants.

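### The between-arm adverse event comparison uses events from any source, but contacts triggered by missed doses exist only in the Pillsy arm, so it can mix detection effort with harm

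*Combined protocol and SAP*

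**What the plan says.** - **The comparison.** Section 6.5 states that "the medical monitor will compare AEs and SAEs between the two arms". Its purpose is given as "We will conduct this analysis to inform the Phase II clinical trial of this intervention". The expected frequency is described only in words ("While we anticipate a very low rate of adverse events"). No summary measure, denominator, test or split by source is given.
- **What is recorded.** Section 5.1.1: "All AEs, whether volunteered, elicited, or noted on physical examination, will be recorded throughout the study". The items required for each AE include seriousness, severity, dates, action, causality and outcome, but not how the event came to light.
- **Scheduled checks.** Table 1 places AE monitoring at baseline and weeks 1, 6 and 12, with no distinction by arm.
- **Contacts in one arm only.** Section 5 (Intervention) says "only the active group will receive the Pillsy app with messaging and reminders". A missed dose produces a text to the named helpers, and the prescriber may be one of them. The synopsis adds: "Providers may decide to call the imminently nonadherent participant to provide a brief, timely therapeutic intervention". It also mentions craving surveys that may be sent. The SAU cap "will track openings but will not provide reminders or any other messaging".
- **Who watches for drug-related events.** Section 5.1.3: "Patients will be monitored by their respective provider for drug-related adverse events". This applies to both arms, but in the Pillsy arm the same provider may also be receiving missed-dose alerts.

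**The concern.** A comparison of AE counts is a comparison of harm only if events are looked for equally in both arms. Here randomised assignment itself adds possible contacts in one arm. Those contacts follow missed doses, when withdrawal, craving or relapse is plausibly more likely to be found. Section 5 also leaves the frequency of office visits to the prescriber, so an alert could lead to an extra visit.

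Two errors are possible. An apparent excess in the Pillsy arm could be better detection. A real reduction in harm could be hidden by it. Either would pass into Phase II planning through section 6.5. If the source is not captured when the event is entered, it cannot be reliably rebuilt afterwards.

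**Working it through.** The plan gives no AE rate, margin or power for safety, so there is no figure of its own to reproduce. The check has three parts.

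**1. Routes of detection by arm**

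| Route | Pillsy | SAU | Where |
|---|---|---|---|
| Scheduled AE monitoring | yes | yes | Table 1 |
| Office visits as the prescriber decides | yes | yes | Section 5, weekly assessments |
| Volunteered or found on examination | yes | yes | 5.1.1 |
| Provider monitoring in usual care | yes | yes | 5.1.3 |
| Clinic records and laboratory data | yes | yes | 4.4; Section 5, Laboratory Assessment |
| Helper text after a missed dose | yes | no | 1.1; Section 5, Intervention |
| Prescriber call prompted by an alert | if designated as helper and chooses to call | no | 1.1 |
| Craving survey | possible | no | 1.1 |

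The arms differ only in the last three rows. The intervals between scheduled checks are (6 - 1) x 7 = 35 days and (12 - 6) x 7 = 42 days. Unequal detection would operate mainly there, although the shared unscheduled routes operate there too.

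**2. Illustrative size, with equal true event rates**

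All inputs are assumptions. Let b be the share of events captured at scheduled visits (0.5 to 0.8), u the share of the rest found by shared unscheduled routes (0.5), and q the share of what then remains found by Pillsy-only contacts (0.25 to 0.5).

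SAU detection: s = b + (1 - b)u. Pillsy detection: p = s + (1 - s)q. Recorded ratio: p / s.

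| b | s | q | p | p / s |
|---|---|---|---|---|
| 0.5 | 0.75 | 0.25 | 0.8125 | 1.08 |
| 0.5 | 0.75 | 0.50 | 0.875 | 1.17 |
| 0.8 | 0.90 | 0.25 | 0.925 | 1.03 |
| 0.8 | 0.90 | 0.50 | 0.95 | 1.06 |

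The range is about 1.03 to 1.17.

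**3. What that looks like with 15 per arm**

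Take SAU detection of 0.8, inside the range of s above, and q = 0.5. Pillsy detection is 1 - 0.2 x 0.5 = 0.9, a ratio of 0.9 / 0.8 = 1.125. Exact binomial enumeration with the same true participant-level risk in both arms gives:

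- True risk 10%: expected participants with a recorded AE are 15 x 0.10 x 0.9 = 1.35 (Pillsy) and 15 x 0.10 x 0.8 = 1.20 (SAU). The Pillsy count is higher with probability 0.40 and lower with probability 0.33.
- True risk 30%: 15 x 0.30 x 0.9 = 4.05 and 15 x 0.30 x 0.8 = 3.60. Higher with probability 0.49, lower with probability 0.34.

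With equal detection the two probabilities would be equal by symmetry. A Fisher test significant at 5% in the direction of Pillsy excess had probability at most 2.8% over all scenarios run (true risk 10-40%, SAU detection 0.6 or 0.8, q from 0 to 0.5).

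**The case against.** Much of the case on the other side stands.

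- **The extra contacts are conditional and are not shown to feed the AE log.** Helper texts may go only to friends or relatives. A prescriber call requires that the prescriber is a helper and decides to call, and it is described as therapy, not as AE collection. Craving surveys are named only in the synopsis. What remains is that 5.1.1 counts an AE however it is learned, so an event disclosed in such a call would qualify. Nor is the helper route marginal: section 4.1 requires every participant to name a partner.
- **A reader might infer that SAU has no route to events between scheduled visits.** Setting u = 0 would give ratios from (0.8 + 0.2 x 0.25) / 0.8 = 1.06 to (0.5 + 0.5 x 0.5) / 0.5 = 1.50. The documents do not support that. Both arms have prescriber visits, volunteered reports, provider monitoring and clinic records.
- **A reader might also infer that the comparison must come out against Pillsy.** That is not established. Retention may differ by arm (it is part of objective 2), and follow-up time changes AE counts in either direction. Craving and drug use are also measured on the same schedule in both arms, and nothing says they are logged as AEs.
- **The setting is small.** This is a 30-person proof-of-concept study with few AEs expected. At 10% risk the illustrated gap is 1.35 - 1.20 = 0.15 of a participant, which cannot be told from chance. This limits the consequence, but does not make the comparison interpretable.
- **Using visit-elicited AEs as the only main comparison could itself mislead,** because it counts only those who attend. This objection shapes the fix.

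**Conclusion.** The point holds as a limit on interpretation. Unequal opportunity to detect AEs is built into the design, and section 6.5 provides nothing to separate it from harm. It matters mainly for non-serious events between scheduled visits. SAEs such as hospitalisation or death are probably less affected.

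Neither size nor net direction can be computed from the documents. The ratio of 1.03 to 1.17 rests wholly on the assumed capture shares and on equal true rates, equal follow-up and equal use of the shared routes. Any effect would act through a descriptive imbalance carried into Phase II, not through a significance test.

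**What to change.** This is an inexpensive improvement in data capture and presentation.

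1. Add a source-of-detection field to the REDCap AE form: scheduled research coordinator visit, clinic visit, alert-driven or app contact, or spontaneous.
2. At weeks 1, 6 and 12, have the coordinator ask the same AE question in both arms about the whole interval since the last visit. Mark every event reported there, even if it was first found another way. Otherwise events first found through an alert would drop out of the Pillsy scheduled-visit count.
3. In section 6.5, present side by side:
   - (a) AEs reported at scheduled coordinator visits, per visit attended, with visits attended shown by arm;
   - (b) all-source AEs by arm and by source.

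   State that an excess seen only in (b) will be read as possible detection.
4. Continue to list all SAEs and report them within 24 hours, whatever the source.

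The cost is one extra field, a standard question and a short addition to 6.5. The downside is that (a) has fewer events and depends on attendance, which is why attendance must be shown and (b) kept beside it. The change does not remove the effect of unblinded questioning.

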7. QUALITY ASSURANCE AND QUALITY CONTROL

7.1 Audit and Inspection

Ideal Option in Spokane, Washington State University, Pillsy Inc and the study documentation, can be subject to quality assurance audit during the study. In addition, inspection may be conducted by regulatory authorities at their discretion.

7.2 Data Management and Coding

Washington State University will be responsible for activities with the data management of this study. This will include setting up a relevant database and data transfer mechanism, along with the appropriate validation of data and resolution of queries. Data generated within this study will be handled according to the relevant procedures outlined by Washington State University and in accordance with several other investigations conducted at Washington State University. Details follow.

7.3 Handling of Protocol Deviation

A protocol deviation is any change, divergence, or departure from the study design or procedures defined in the protocol. Protocol deviation will be handled in accordance with the Washington State University IRB (www.irb.wsu.edu). If a protocol deviation occurs, corrective actions will be implemented promptly.

8. ETHICS

Training Requirements

Human Subjects CITI Training

All Research staff will complete online training through The Collaborative Institutional Training Initiative (CITI) <https://about.citiprogram.org/en/homepage/>, a web-based training program on Human Research Subject protections, before starting the study training.

Study Training

All RCs and Research Associates or Research Assistants will complete all the following before interacting with participants:

Thoroughly read the protocol and guidelines on consenting and safety procedures found below. RC should be knowledgeable on all procedures and safety procedures. This includes HIPAA training. Documentation of course completion will be included in the study file.

Practice all study procedures & consenting with existing study personnel. All study staff should be able to answer common questions from participants.

Shadow and watch an approved RC complete an entire study visit: recruiting, consenting, and randomizing with a participant.

Receive approval by the Principal Investigator.

Informed Consent

General Guidance for Informed Consent

Human subjects research at Washington State University is coordinated through the Washington State University Institutional Review Board (IRB). The IRB is responsible for the review and approval of all research activities involving human subjects. The IRB is charged with protecting the rights and welfare of human subjects to ensure that all study participants are treated physically, psychologically and socially in such a way as to minimize embarrassment and stress and to avoid harm or other negative effects.

The process of obtaining informed consent is a basic ethical obligation and a required element of human subject research. The IRB will require that informed consent be documented using an electronic written consent form approved by the IRB and signed and dated by the subject. The participant will be given ample time to read the consent document before it is signed.

Participants will be asked to type in their name and date for the consent electronically. A copy of the document will be made available to the person signing the form.

The informed consent form will be presented to allow potential participants to review facts about the study and what will be asked of them so that they can voluntarily choose whether to participate as a research subject.

Changes to the study protocol may result in the need for a new consent form. Only the approved and most recent consent form will be used. The consent form document will have an IRB stamp of approval, version number and date at the bottom each page.

Please note: Unless you have the PI's authorization, do not conduct the consenting process.

Consenting Process:

1. The consenting process will be conducted in a consistent manner for every potential participant.
2. If participant is eligible, the iPad that was used for screening will display the consent form. RA or RC will explain that this document will explain the details of the study they are being asked to take part in. Allow the participant plenty of time to read.
3. When the participant is done reading the consent, they will be asked if they have any questions about the study. All questions will be answered before the participant signs the informed consent document. The consent form will then be thoroughly reviewed to ensure that the participant understands what they are agreeing to. Participants will be asked to type in their name and date for the consent electronically, and actually sign their name electronically.
4. Eligibility for the study is determined by study procedures. Signing the consent does not ensure eligibility to participate. That said, it will be made clear to the prospective participant that participation will not impact their care.
5. The most key point to stress in the consenting process is that participation is voluntary. Moreover, continued involvement in the study is also voluntary. Participants can choose not to consent to the study or discontinue at any time for any reason. They can choose not to answer any questions that make them feel uncomfortable.
6. Show the participant where to type their name and date the consent form. The participant must date and initial the consent and be offered a paper copy of the consent to the participant for their records.
7. Remember that consenting is an ongoing process.

SUICIDAL & HOMICIDAL IDEATION/BEHAVIOR

If a person reveals SUICIDAL IDEATION (in the last 30 days) at any level or during the screening:

1. Staff will explain their concern for the subject and inform their supervisors.
2. All current (last 30 days) suicidal ideation and behavior concerns will be immediately reported to "911" or appropriate clinic staff so that their protocol can be initiated.

